**Data collection:** Gynecologists will be recruited through direct referral (from AL ACOG and UAB OB/GYN Center for Research) either through email correspondence or direct communication. A prescreening electronic query that will identify whether they meet inclusion criteria will be given through email correspondence, followed by consent. Data will be collected using a secure electronic server and will be designed to only last approximately 15 minutes. Surveys will include sociodemographic variables and validated scales to determine HIV/PrEP knowledge, HIV/PrEP stigma as well as questions to ascertain current routine testing and screening practices.

**Power Calculations and sample size considerations:** We will administer our survey to 250 Alabama gynecologists. This sample size will allow us to detect odds ratios of willingness to prescribe PrEP of 2.09 for binary variables (50% in each group across study) and 1.47 for a standard deviation change in continuous variables assuming 80% power, 30% baseline percentage of willingness to prescribe PrEP, no other variables in the model, and Type 1 error rate of 5%. When covariates are included that have a correlation of 0.2 with the independent variable, the detectable ORs increase (2.27 and 1.54 respectively for binary and continuous variables).

**Primary outcome:** Willingness to prescribe PrEP (categorical, yes vs no).

**Secondary outcome:** Belief clinical-setting capable of providing PrEP services (ordinal, 1-10)

**Independent variables:** Expected variables as listed in *Table 2*.

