**Table 2. Expected Independent Variables, RE-AIM Constructs**

Independent Predictor Variable	RE-AIM Construct	Measures
Clinical-setting level - Determine denominator (i.e. number of providers in clinical settings) willing to prescribe PrEP and factors associated with their willingness - Determine belief current clinical setting prepared to provide PrEP services	Adoption	- Socio-demographics: race/ethnicity, clinic name, gender, years of practice, clinic resources, characteristics of populations served - Knowledge: PrEP and HIV - Stigma: PrEP and HIV - Practice: Sexual history, STI testing, STI treatment

**Descriptive statistics:** Frequencies for reported willingness to prescribe PrEP will be reported overall and for each independent variable. Descriptive statistics (median/interquartile ranges, frequencies/percentages) and comparisons between those willing to prescribe PrEP and not willing will be reported for each independent variable in bivariate logistic regressions. Multivariable logistic regression models will be performed adjusting each independent variable by a priori variables, such as age, race and sex, and other variables included based on literature review.

**Logistic regression analyses:** Bivariate models will be fit and variables with p-values  $\leq 0.1$  will be included in multivariable logistic regression analyses. Model fit will be determined using Hosmer and Lemeshow tests. A priori variables will be selected and included based on literature review.

**Sub-aim 2:** To further assess individual-level determinants, we will conduct focus groups with Black cis-gender women living in Alabama to explore desired PrEP educational materials and communication strategies from gynecologic care teams.

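### Aim 1 gives two unreconciled model rules for willingness to prescribe PrEP; if the p≤0.1 screen governs, it exaggerates weak or null determinants that pass, and intervals for null ones under-cover

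*Combined protocol and SAP*

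**What the plan says.** The passages are in the protocol, Specific Aim 1, Sub-aim 1 (quantitative survey).

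- Power Calculations: "We will administer our survey to 250 Alabama gynecologists". The stated assumptions are "assuming 80% power, 30% baseline percentage of willingness to prescribe PrEP, no other variables in the model, and Type 1 error rate of 5"%.
- Descriptive statistics: the multivariable models work by "adjusting each independent variable by a priori variables, such as age, race and sex", plus others from the literature. No p-value decides which predictors are reported.
- Logistic regression analyses: "Bivariate models will be fit and variables with p-values" of 0.1 or below go into the multivariable analyses. The paragraph ends: "A priori variables will be selected and included based on literature review".
- Table 2 lists about 11 to 13 measures, depending on how they are counted. They cover provider and clinic characteristics, PrEP and HIV knowledge and stigma, and sexual-health practice. Years of practice is listed; age is not.
- The PrEP4Her Analysis Plan deals with Specific Aim 3 only.

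**The concern.** Both paragraphs describe the multivariable analysis of the same outcome. Under the first, every predictor receives an adjusted estimate. Under the second, a predictor outside the a priori set receives one only if its crude association reaches p≤0.1. A reader of the results could not tell which rule produced a given odds ratio, or whether a missing predictor was never modelled or was screened out. The a priori set is also left open.

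If the second rule governs, selection and estimation use the same data, and the final p-values and intervals make no allowance for the selection. A weak determinant is reported mainly in surveys where chance made it look strong. A null determinant is reported only when chance made it look non-null. These survey results are among the inputs to choosing the barriers that PrEP4Her should address.

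**Working it through.** **Inputs.** From the protocol: N = 250, 30% willing (250 × 0.30 = 75 providers), two-sided 5% (sidedness is not stated, but two-sided reproduces the figures), 80% power, entry at p≤0.1. Assumed, because the documents do not give them: number of predictors (10 to 13), pairwise correlation (0 or 0.2) and true odds ratios.

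**Step 1: the plan's own figures.**

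- Continuous: the plan's figure is "1.47 for a standard deviation change in continuous variables assuming 80% power". SE of the log OR per SD = 1/√(N·p·(1−p)) = 1/√(250 × 0.30 × 0.70) = 1/√52.5 = 0.138. Detectable OR = exp[(1.960 + 0.842) × 0.138] = exp(0.387) = 1.47. Reproduced.
- Binary: the plan says that it can "detect odds ratios of willingness to prescribe PrEP of 2.09 for binary variables (50% in each group across study"). Taking 125 against 125, with 30% in the reference group, OR 2.09 corresponds to 47.2% in the other group and gives 80.4% power. Reproduced.
- With covariates, "the detectable ORs increase (2.27 and 1.54 respectively for binary and continuous variables"). These reproduce (2.266 and 1.541) if 0.2 is read as R². A correlation of 0.2 (R² = 0.04) gives 2.11 and 1.48. That is a separate matter and does not affect this point.

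**Step 2: what the screen does to a single continuous predictor.** To pass two-sided p≤0.1, the estimate must reach exp(1.645 × 0.138) = exp(0.227) = 1.25 per SD, or its inverse. A true OR of 1.20 lies below that threshold, so it can pass in the right direction only when overestimated. In the normal approximation, conditional on passing:

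| True OR per SD | Passes | Mean OR if passed | 95% interval coverage if passed |
|---|---|---|---|
| 1.00 | 10% | no net direction | 50% |
| 1.10 | 18% | 1.31 | 81% |
| 1.20 | 37% | 1.38 | 93% |
| 1.47 | 88% | 1.52 | 97% |
| 2.00 | 100% | 2.00 | 95% |

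The 50% follows directly: a null predictor passes with probability 0.10, its interval excludes OR 1 with probability 0.05, and (0.10 − 0.05)/0.10 = 0.50. Among 12 independent null predictors, 12 × 0.10 = 1.2 are expected to pass, and the chance that at least one does is 1 − 0.9^12 = 72%.

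**Step 3: screen then fit, by logistic simulation at N = 250 and 30% willing.**

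| Scenario | Mean OR of a real effect when selected (coverage) | Coverage, selected nulls | Unscreened comparator |
|---|---|---|---|
| 13 predictors, all null, r = 0.2 | – | 67–69% | – |
| 13, one OR 1.20, r = 0.2 | 1.33–1.34 (95–96%) | – | full model 1.22 (95%) |
| 12, three OR 1.20, r = 0 | 1.40 (92%) | 53% | full model 1.21 (94%) |
| 12, three OR 1.20, r = 0.2 | 1.29 (97%) | 88% | full model 1.21 (94%) |
| 12, three OR 1.47, r = 0 | 1.55 (97%) | 55% | full model 1.51 (95%) |
| 12, three OR 1.47, r = 0.2 | 1.44 (96%) | 97% | full model 1.51 (94%) |
| 10 candidates plus 3 a priori covariates forced in, true OR 1.20 or null | 1.37–1.39 | 48–69% | first rule 1.20 (about 95%) |

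The last row matters most. It uses the reading in which the a priori variables stay in the model whatever their p-value, and it compares the two rules that the protocol itself states.

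**Step 4: does the screen create more false determinants?** In the all-null case with 13 predictors, 1.26 pass per survey and 36% of those reach p<0.05: 1.26 × 0.36 = 0.45 significant nulls per survey. Testing all 13 at 5% gives 13 × 0.05 = 0.65. The count does not rise.

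**The case against.** Several objections stand and limit the point.

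- A reader might call the two rules incompatible. The closing sentence of the screening paragraph allows a combined reading: a priori variables forced in, screened variables added. The fault is that no primary model is named. For the same reason it cannot be said that the screen drops confounders named a priori. Bivariate results are also reported for every predictor, so screened-out variables remain visible.
- A reader might infer that all reported intervals are too narrow. They are not. Real effects of 1.20 keep 92% to 97% coverage when selected, and their problem is exaggeration. Serious under-coverage is confined to null or near-null predictors, and it fades (88%, 97%) when several correlated real effects are present.
- A reader might infer a larger number of spurious barriers. Step 4 shows otherwise.
- Comparing a mean given selection with a mean over all fits favours the unscreened model. Among results with p<0.05, in the scenario with one true OR of 1.20, the screened model averages 1.45 and the full model 1.52. An unscreened analysis therefore helps only if every predictor is reported, not just the significant ones.
- Aim 2 has no rule based on an odds ratio or p-value. The planning group reviews the survey together with interviews and focus groups, and advisory board feedback can change components.
- The age point is minor: Table 2 lists expected variables, and the survey is said to collect sociodemographics.

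What remains is that the protocol does not say which rule governs, and that one of them distorts what is reported for weak and null determinants even with the a priori covariates kept in.

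**Conclusion.** The point holds in this limited form. Two rules for the same outcome are unreconciled and the analysis plan does not settle them. If the p≤0.1 screen governs, then with few or no real effects a true OR of 1.20 per SD is reported at about 1.34 to 1.39 when selected, which is 12% to 16% too high (1.34/1.20 and 1.39/1.20). Single runs ranged from 1.33 to 1.40, and three correlated real effects gave 1.29. Coverage for nulls that pass is about 50% to 70%. At the powered OR of 1.47 the effect is small: 1.52 in the normal approximation, and 1.55 against 1.51 unscreened with uncorrelated predictors. These sizes rest on assumed predictor numbers, correlations and effects. The documents do not support saying that Aim 2 components will be chosen on false odds ratios. They do support saying that weak survey determinants may look stronger than they are to the group that reviews them.

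**What to change.** In Specific Aim 1, merge the two paragraphs and name one primary analysis, using the protocol's own first rule:

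- Fit each Table 2 predictor in a logistic model adjusted for one fixed, listed covariate set, chosen before the outcome data are examined (or, if they have been, with that stated).
- Report every predictor's odds ratio and interval, whatever its bivariate p-value.
- Delete the p≤0.1 screen, or label that model exploratory and state that its intervals do not allow for selection.
- Keep age in the covariate set only if the survey collected it; otherwise remove it.

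The estimates will then be associations adjusted for the covariate set, not for all the other predictors, and the report should say so.

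Cost: wording, or a reporting decision if the survey is already complete. Sample size and procedures do not change. There are more estimates to present, and intervals for some predictors may be slightly wider.

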### **Specific Aim 2. Develop and refine a multi-component implementation strategy (PrEP4Her) to integrate PrEP in gynecology clinics using formative data from Aim 1 and a process of community-engaged research.**

#### **Study Design: Intervention**

#### **Mapping Approach.**

We will work with our CAB and draw on Intervention Mapping (IM) techniques to guide translation of our Aim 1 results into a protocol for development of our implementation strategy with subsequent piloting in Aim 3. IM is an established process for systematically developing behavior change interventions, with iterative paths from problem identification to problem implementation (**Table 3**). We have chosen to use this process to select components for our implementation strategy, because

*the ultimate goal of this study is to change behavior of both providers and patients during routine GYN clinic visits.* IM highlights the importance of incorporating data to map out the problem (i.e., PrEP underutilization by Black cis-gender women), its determinants (better refined in Aim 1), and potential implementation strategy components to facilitate identified goals. Specifically, Aim 2 will focus on Steps 1-4, which are the most relevant steps to intervention development. In Step 1 – we will work with our planning group (the CAB and study team) and review the findings from Aim 1, identifying key barriers we feel need to be addressed among Black cis-gender women and providers. In Step 2 – we will create a logic model of change, in which we focus on objectives, smaller goals than the larger overarching goal of improving PrEP prescriptions for Black cis-gender women. In Step 3 – we will map out our implementation strategy components based on the logic model of change, and begin to link them to desired implementation outcomes (e.g., job aids, educational materials for Black cis-gender women, etc.). In Step 4 – we will develop specific content implementation strategies.

**Proposed PrEP4Her Implementation Strategy Components:** The development of the PrEP4 Her Implementation Strategy begins with components already identified in existing studies where PrEP was implemented into family planning clinics in the South. Aim 1 findings will then be used in Aim 2 to refine this initial list, by either eliminating unnecessary components, adding additional ones, or adapting existing

**Table 3. PrEP4Her Mapping Protocol** (adapted from Bartholomew)

Step 1: Logic Model of the Problem	
 
Review and identify key barriers to PrEP implementation in GYN settings
 
State evidence-based practice goals
 

Step 2: Program Outcomes and Objectives; Logic Model of Change	
 
Specify PrEP4Her objectives
 
Select key determinants for behavioral outcomes that need to be addressed
 
Construct matrices of change through select ecological levels (i.e. individual through societal)
 

Step 3: Program Design	
 
Choose components of implementation strategy to address determinants
 

Step 4: Program Production	
 
Refine components of implementation strategy
 
Prepare plans for program implementation
 
Draft & Pre-test materials and protocols
 

Step 5: Program Implementation Plan	
 
Identify potential program users
 
Construct matrices of change objective; program use
 
Design Implementation intervention
 

Step 6: Evaluation Plan	
 
Write effect and process evaluation questions
 
Develop indicators and measures for assessment
 
Specify and complete evaluation design/plan
 

components to respond to the unique GYN context. In Table 6, we have provided our hypothesized name, definition and operationalization of components based on the guidelines established by Proctor et al., in terms of seven dimensions of specificity, including: 1) actor (who delivers the strategy), 2) action (steps or processes to be taken), 3) target (what will be impacted by the strategy), 4) temporality (the order or sequence of the strategy), 5) dose (intensity or amount of time spent for a strategy), 6) implementation outcomes affected (grounded and RE-AIM and included constructs from Procter et al) and 7) justification (rationale for selected components).

**Table 4. Specification of Hypothesized Components of Implementation Strategy (“PrEP4Her”)**

[figure not shown]
Named PrEP4Her components	1. Universal sexual health screening for GYN patients 2. Synchronous Training of GYN care team on HIV, PrEP indication, PrEP care (for both daily and long-acting injectable regimens), and stigma 3. PrEP indication job aids 4. Electronic medical record documentation aids, including pre-templated notes and order sets	5. Educational materials for Black cis-gender women on HIV and PrEP 6. Asynchronous training on effective communication strategies with patients about sexual health and PrEP				
Implementation Strategy	Number 1	Number 2	Number 3	Number 4	Number 5	Number 6
Actor	Medical assistant or care provider	Study staff/ PrEP expert	PrEP expert	PrEP expert and information technician	PrEP expert and graphic designer	PrEP expert
Action	Charts evidence based sexual history questionnaire in the medical record 	Provides 1.5 hour training on HIV, risk, and PrEP indications and care	Creates easily accessible pocket cards with indications for PrEP 	Creates templates in electronic medical record for PrEP visits and order sets	Develops informational content to include in educational materials tailored to Black cis-gender women	Develops 15-30 minute training tutorial on how to communicate with patients about sexual health and PrEP, tailored to Black cis-gender women
Target	Patient	Providers/staff	Provider	Provider	Patient	Patient
Temporality	Medical assistant – Before every patient encounter with a provider OR Provider – Beginning of every visit	1-month prior to PrEP4Her being implemented at our pilot site	Continuously carried by providers and displayed in shared workspaces	1-month prior to PrEP4Her being implemented with instructions on how to access placed in shared workspaces and sent through email communications	Placed in waiting areas and/or private exam rooms, accessible during every visit and replenished by study staff	1-month prior to PrEP4Her being implemented and presentation accessible in shared work space as well as emailed to all providers
Dose	5-minute screener at every visit	1.5 hour training occurring once prior to 6-month pilot	As needed by providers during clinical care	As needed by providers during charting	Available during the entire 6-month pilot for every clinic	Once prior to 6-month pilot and then available as needed
Implementation Outcomes affected	Please see Figure 2. for detailed description of how each implementation strategy maps to implementation outcomes. In short, we will be evaluating the following proximal implementation outcomes: reach, adoption, fidelity, acceptability, and preliminary effectiveness. Distal outcomes will not be evaluated in this study.					
Justification	Implementation strategy components selected for this study have been selected based on observed, researched or hypothesized barriers based on review of the literature. These components may be subject to change based on findings in Aim 1 and feedback from our CAB.					

**Pilot intervention development with CAB:** We will engage members of our CAB, including key stakeholders in GYN clinic operations, care and management as well as Black cis-gender women (aged between 18-45) bi-weekly over a 3-month period of time (see structure above). During this time, we will conduct IM (outlined above) and pilot materials developed as a part of selected implementation strategy components. After implementation strategy materials have been refined, we will review appropriate operational steps needed to integrate PrEP into our clinical site. For implementation strategy selection and content development, we will work closely with [name] who has expertise in implementation science working with family planning clinics in Southern settings to improve HIV prevention among Black cis-gender women. We will meet with [name] monthly, in one-hour meetings with a consultation fee of \$100/hour. (See Letter of Support)

**Specific Aim 3. Pilot PrEP4Her, refined through Aim 2, to deliver PrEP for Black cis-gender women attending routine gynecologic care visits.**

**PrEP4Her Study Design:** PrEP4Her, a multi-component implementation strategy with components defined as well as refined through prior aims, will be evaluated through a one-arm pilot at a university-affiliated GYN clinic. (**Figure 3**) We have chosen a one-arm trial because PrEP is not currently being offered routinely at GYN clinics and there are three Black cis-gender women on PrEP in the university-affiliated PrEP clinic, making a comparison either between other GYN clinics or between our PrEP clinic have limited meaning. Implementation processes will result from communication with our CAB and consultant ([name]). Upon completion of PrEP4Her development, we will begin engaging key GYN staff, practice managers and clinicians to begin training as well as implementing job and documentation aids within the clinic. Educational materials will be placed in all areas where patients are seen within the clinic. We will monitor implementation outcomes for PrEP4Her over a 6-month timeframe, with detailed procedures that we have described in the below section.

**Figure 3. PrEP4Her Predicted Workflow**

**PrEP4Her Components**

1. Universal Sexual History – Brief, gender-neutral sexual history screening assessment. 	3. Job Aids – 2-sided pocket cards for white coats/scrubs that will include CDC guidance summary criteria for PrEP in cis-gender women and 5Ps. 	5. Educational Materials – Pamphlets, tailored for Black cis-gender women that contain information about HIV and PrEP. 
2. Synchronous HIV and PrEP Training – ~ 1.5 hour PrEP informational training (adapted from [name] et al. in family planning clinics) made available on UAB CFAR website. 	4. EMR Documentation/Order Aids – Premade order sets within UAB electronic medical record for initial and 3-month PrEP visits as well as a PrEP note template.	6. Asynchronous Training on Communication Strategies – ~ 15 minute training on communicating empowering, “gain-framing” messaging, made available on CFAR website. 

**Procedures for Evaluating Proximal Implementation Outcomes:**

**Reach Outcome:** For this study outcome, Reach (i.e. the number of individuals who are willing to participate in an initiative) is defined as the absolute number of Black cis-gender women who receive a PrEP prescription. We will also evaluate the proportion of women prescribed PrEP who had a PrEP indication. PrEP indication will not be defined using the Center for Disease Control and Prevention (CDC) PrEP indication clinical guidelines due to evidence suggesting these criteria are too restrictive and may not predict risk. Instead we will define PrEP eligibility based on the CDC’s guidance summary criteria, deeming those PrEP eligible who meet any of the following criteria for cis-gender women not living with HIV (over a 6-month timeframe): HIV-positive sex partner, bacterial STI (gonorrhea or syphilis), more than one sex partner, inconsistent condom use, sex for exchange of goods, or being in a high-prevalence network. This data will be obtained based on the sexual risk screener (a component of implementation strategy) documented in the chart during patient visits.

**Procedures.** Data will be collected from the university’s electronic medical record, looking at visit data for all cis-gender women with clinic visits during the pilot timeframe. We will be able to extract prescription data directly, but PrEP eligibility and referral will require review of chart documentation.

**Preliminary Effectiveness Outcome:** To evaluate effectiveness of PrEP4Her, we will determine increases in PrEP prescriptions over-time. We will also evaluate what patient factors are associated with PrEP prescription.

**Procedures.** A data extraction of the UAB electronic medical record will be done (as described above) at 3-month time intervals after implementation of PrEP4Her (i.e. baseline, 3-months and 6-months’ time). We will collect the following patient demographics: age, race, ethnicity, and insurance status.

**Statistical analysis.** Frequencies for prescription will be reported overall and for each independent variable (i.e. patient demographics), at each of the 3 time points (baseline, 3 months and 6 months). Means, standard deviations and t-test comparisons between those referred and prescribed PrEP will be reported for continuous

independent variables if normally distributed. For variables with excessive skewness or otherwise non-normal distribution, medians with upper and lower interquartile ranges will be reported compared by Wilcoxon rank sum test. Categorical independent variables will be reported as frequencies and percentages and compared by chi-square and Fisher's exact test. Bivariate models will be fit and variables with p-values  $\leq 0.1$  will be included in multivariable logistic regression analyses. Model fit will be determined using Hosmer and Lemeshow tests.

**Adoption Outcome:** As a dimension within the RE-AIM framework, we define adoption as the proportion of key-stakeholders within our pilot site who were willing to initiate our implementation strategy. In order to assess this, we will conduct and document the following procedures.

**Procedures.** Trainings: During synchronous trainings we will document the number of providers and staff who attend meeting. Asynchronous attendance will be captured through collecting para-data (to track clicks) on the number of providers and staff who visit the CFAR website and access training materials. Additionally, we will connect a REDCap survey link to the end of training materials that will include a single-item asking "Did you access these training materials to aid in PrEP implementation at the UAB GYN Continuity Clinic?". Sexual History: We will conduct a chart review (similar to what was described above), to evaluate absolute number of patients seen during our pilot timeframe who had a sexual history taken.

**Acceptability Outcome:** We are defining acceptability as the extent to which key stakeholders, both provider delivering the intervention and Black cis-gender women receiving it, felt PrEP4Her was acceptable. In order to assess this, we will conduct key-informant interviews with stakeholders.

**Sample.** Key informants will include 15-20 stakeholders from our pilot site (including approximately 10 providers, managers, and other support staff), as well as Black cis-gender women (approximately 10-15) who were seen during the 6-month intervention pilot.

**Recruitment.** We will recruit key stakeholders directly from our pilot site and Black cis-gender women will be recruited after the pilot through flyers and direct referral from clinical staff.

**Procedures.** Interview guide questions will be grounded in a theoretical framework of acceptability from Sekhon et al., including seven constructs. (See **Table 5**) Interviews will conducted virtually, to allow for flexibility of clinical staff using a secure system. All interviews will be digitally audio recorded, professionally transcribed and de-identified.

